## 9.2.2 Intervention

### Patient intervention overview (both arms)

We will use a low-calorie approach from our previous studies.(39, 67) The diet will consist mainly of whole-grain, complex starches, vegetables, fruits, lean meats, and low-fat dairy products.(68, 69) The goal for total caloric intake, which will be personalized for each patient, will be calculated by subtracting 500-1000 kcal from the maintenance energy requirement determined by a sex and overweight/obesity-specific outpatient formula.(70) The range is

provided to encourage participants to stay under the 500 kcal deficit level in order to lose weight at an adequate rate but above the 1000 kcal deficit level, which may require closer medical monitoring. If a participant experiences a prolonged plateau after a previous downward weight trajectory, then energy intake may be reduced further by 300-500 kcal per day. If a participant achieves goal weight before the end of the 6-month initiation period, then energy intake will be adjusted to maintenance-level calories. At the end of the initiation period, all patients will be provided with a personalized maintenance-level calorie budget.

Patients will be guided to achieve the current recommendations for physical activity. The 2018 current Guideline recommends at least 150 minutes per week of moderate-intensity aerobic physical activity such as brisk walking.(71) We acknowledge that some individuals will not meet recommended guidelines. Consistent with national recommendations, they will be encouraged to do as much as they can since bouts of moderate to vigorous exercise of any duration have been found to be beneficial. (71) Additionally, in accordance with the American College of Sports Medicine guidelines, we will recommend 2-3 days per week of muscle strengthening activities and stretching. (72) We will emphasize that between 150-250 minutes per week of moderate intensity exercise is recommended for weight loss, with greater weight loss achieved with more minutes of exercise and >250 minutes needed to maintain weight loss and prevent regain.(73) One group session (in month 5) will be devoted entirely to physical activity. Additionally, 15 minutes of each of the other sessions will be devoted to educating, demonstrating, and performing exercises, such as a walk, a muscle strengthening routine that can be done in the home without equipment (e.g., chair stands), and a stretching routine. The content of physical activity education, which can occur during didactic session or during the 15-minute exercise demonstrations, will encourage increased self-efficacy, awareness of health benefits, reduction of barriers, increased enjoyment, identification of strategies to overcome relapse, and development of personally meaningful incentives and reinforcements for successful physical activity engagement. Collectively, these are associated with initiation and maintenance of physical activity.(74) An overview of patient weight loss initiation and maintenance interventions is provided in Table 3.

Table 3

		Patient	Patient + Partner
Month	Mode	Weight Loss Initiation	
		Content	Additional Content
1	G, IP	Randomization Disclosure Introduction to Low-Calorie Diet	
1	G, IP	Interpreting the Food Label SMART Goals	Orientation to Diet Role of Partner Shared Decision Making
2	G, IP	Importance of Tracking Diet & Activity Setting a Goal Weight	Sharing Thoughts and Feelings
2	G, IP	Grocery Shopping and Grocery Store Tour	
3	G, IP	Meal Planning: Setting Up for Success	Role plays Couple conversations focused on support for dining out
3	G, IP	Healthy Cooking & Modifying Recipes	
4	G, IP	Dining Out	Role plays Couple conversations focused on support for dining out
4	G, IP	Dining Out: Advanced	
5	G, IP	Physical Activity	Role plays Couple conversations focused on support for physical activity
5	G, IP	Eating More Fruits and Veggies	
6	G, IP	Mindful Eating	Role plays Couple conversations focused on support for mindful eating
6	G, IP	Emotional Eating	
6	G, IP	Weight Loss Review and Potluck	
Weight Loss Maintenance			
7	G, IP	Maintaining Weight Loss	Role plays Couple conversations focused on support for weight loss maintenance
7	I, T	Behavioral Maintenance Intervention	Support plan, problem-solving
8	G, IP	Habits of successful losers	Role plays Couple conversations focused on support for healthy habits
8	I, T	Behavioral Maintenance Intervention	Support plan, problem-solving
9	G, IP	Relapse Prevention	Role plays Couple conversations focused on support for high-risk social situations and relapse prevention Review of couple communication skills
9, 10, 11, 12, 14, 16, 18	I, T	Behavioral Maintenance Intervention	Support plan, problem-solving (only in months 9, 12, 18)

G, IP=group, in-person      I, T=Individual, telephone

### Patient weight loss initiation intervention (months 1-6, both arms)

Groups of ~11-12 patients will meet every 2 weeks and will be led by an interventionist. Meetings will begin with weigh-ins by research staff (self-report weight photos may be collected via a DOS REDCap link if group classes are delivered remotely and participants will be mailed a scale in this situation) and will involve dietary education, physical activity demonstration, and goal setting. Partners in the partner-assisted arm will attend a subset of these sessions, whereas partners in the patient-only arm will not be permitted to attend group sessions. The group sessions may be delivered via a video call if necessary due to public health measures that would prevent classes from happening in-person. Patients will download the MyFitnessPal application to their mobile phones, to promote

self-monitoring of diet. Although patients will be recruited in Madison, WI, where the PI is located, data from the Fitbit™ will be transmitted to Prompt, a mobile health platform developed by the Duke Digital Health Institute. Using Prompt will save time and money that would be needed to develop a similar resource at UW. Study staff will assist patients during the first group meeting with installing the apps and will be available for ongoing support throughout the trial.

We have reported the theoretical orientation of the initiation and maintenance interventions.(75) The constructs and way they are operationalized are summarized in Table 4. Although the didactic content varies across contacts, the same initiation behavioral strategies are taught and practiced in each group session in months 1-6, and the same maintenance strategies are taught and practiced in each contact in months 7-18. Our model addresses social support during initiation and maintenance.(75) During initiation, patients in a group-based weight loss intervention may receive support from two sources: (1) the intervention setting (interventionist, group members) and (2) their existing social network (friends, family, coworkers). Regarding (1), patients in both arms may derive support from the intervention setting. Regarding (2), in the patient-only arm, patients will not receive instruction on how to solicit social support and partners will not receive intervention. In the partner-assisted arm, couples will receive training in how to engage in communal coping. All the in-person group sessions will be audio recorded.

Table 4

Initiation	Maintenance
Goal setting/action planning to enhance action self-efficacy 
 
Set 6-month weight loss goal (1-2 lb/week)
 
SMART goal setting led by RD at each group session
 
	Relapse prevention planning to enhance maintenance and recovery self-efficacy 
 
Identify high-risk situations for lapse
 
Generate relapse prevention plan
 
Review and update plan
 

Monitoring by self and interventionist Self 
 
Weight: scale
 
Diet: MyFitnessPal
 
Physical activity: Fitbit™
 
 Interventionist 
 
Weight: weigh-in at group sessions
 
Diet and physical activity: Interventionist will do informal check-ins
 
	Monitoring by self 
 
Weight: scale 
 
Specify day frequency, day of week, time of day for self-weighing
 
Set threshold that indicate relapse (+3 pounds)
 
 
 
Diet and physical activity: re-initiate via MyFitnessPal and Fitbit™ if relapse occurs
 

Favorable expectations about future outcomes of the behavior change 
 
Write letter to self, describing struggles with weight, anticipated outcomes
 
	Satisfaction with outcomes of the behavior change 
 
Review before and after pictures, letter to self
 
Reflect on satisfaction in several domains (e.g., fit of clothes, mobility)
 

Social support derived from social network, interventionist, and similar others 
 
Participation in group conversations
 
Verbal reinforcement from study team
 
	Social support derived from social network 
 
Designate primary support person (partner, sibling, adult children, friend, coworker)
 
Review how that person provides support
 

#### **Patient weight loss maintenance intervention (months 7-18, both arms)**

Patients will transition to the behavioral maintenance intervention in month 7 regardless of whether they achieved their 6-month weight loss goal for 3 reasons: 1) It is not feasible for some patients to continue the group-based initial protocol while others transition to the individual maintenance protocol; 2) Based on previous studies, most patients achieve maximum weight loss at 6 months; 3) Our maintenance protocol allows for patients to continue pursuing weight loss during the maintenance phase if desired. The protocol also stipulates that patients who relapse (gain > 3lb.) should revert to creating dietary and physical activity goals and monitoring these behaviors, thus re-focusing on weight loss. In months 19-24, patients will not receive intervention but will be encouraged to continue self-monitoring using the provided devices. This transition mimics real-world practice in which patients would be expected to apply the maintenance skills they have learned once intervention contacts cease. The 6-month period without intervention contact will allow examination of the sustainability of intervention effects.

The maintenance intervention was designed to help patients transition from the intensity that characterizes most weigh loss interventions to the real world in which patients rarely have further intervention-related contact. This intervention involves a shift from diet initiation content to maintenance-oriented skills training, then switches mode from in-person to telephone, and finally decreases contact frequency. The interventionist will place all telephone calls using a semi-structured script programmed into a custom intervention program that records participant responses for reference in subsequent calls. There will be a 2-week window around the target call date. If the educator is unable to contact a patient in the call window, then that telephone call will be skipped. Continuity will be maintained because each call involves a review of data from the previous call and a review of the same behavioral skills. All maintenance telephone calls will be audio recorded. [name] will meet with [name] and the interventionists weekly to review a random subset of recorded calls and provide feedback using a checklist.

### **Partner intervention overview (partner-assisted arm)**

The theoretical basis for the partner intervention is Lewis' interdependence model (Table 5), along with principles of cognitive-behavioral couples therapy.(76) Cognitive-behavioral couple therapy (CBCT) is an empirically supported, efficacious intervention for both preventing and treating relationship distress. A central feature of CBCT is communication skills training, which focuses on teaching couples skills for effectively sharing their thoughts and feelings, listening supportively to each other, and making decisions together. Our intervention incorporates treatment components of evidence-based, couples interventions for medical problems specified by Baucom, Porter, et al.(46) to target key processes in the interdependence model (Table 5). We will train couples in communication and support skills and help them apply these to 1) increase their perception of weight loss as "our problem" (transformation of motivation") and 2) enhance partners' efficacy and abilities to engage in communal coping and support patients' weight loss efforts in a way that is mutually acceptable and satisfying (communal coping processes).

**Table 5**

Interdependence Construct	Operationalization
Transformation of motivation	
 
• Psychoeducation and discussion about (1) health effects of obesity and (2) interdependence of patient and partner diet and physical activity behaviors
 
• Patients and partners sharing their thoughts and feelings about how obesity affects their relationship
 
• Communication skills training
 

Communal coping process	
 
• Joint action planning
 
• Joint relapse prevention planning
 
• Identifying and practicing methods of providing informational, emotional, and instrumental support (e.g., complimenting on changing habits, exercising together)
 

### **Partner involvement in weight loss initiation intervention (months 1-6)**

The partner intervention will be delivered by the interventionist and, as explained in C.9, will be supplemented with text messages to reinforce support principles and support commitment. There is no literature to suggest the optimal dose of a partner intervention. We are using our experience in dyadic interventions to strike the balance between efficacy and burden, which will be achieved by a combination of partners participating in a subset of group and telephone patient intervention contacts and receiving supplemental text messages. Partners are not requested to attend all 12 biweekly patient sessions, as burden may lead to attrition. Instead, they will attend 6 monthly meetings. Monthly contacts led to meaningful patient behavior change in our previous trials. The month 1 partner meeting will be conducted at the same time as the patient meeting with the goals of orienting partners to the intervention, introducing social support principles, and providing example behaviors that are likely to be perceived as bilateral and supportive versus unilateral and unsupportive. For example, partners will be taught to provide empathy and avoid making comments that can be perceived as critical; comment on positive rather than negative patient behaviors; make the same lifestyle changes when possible; offer praise; and help patients reward themselves for goal achievement.

In months 2-6, partners will attend monthly sessions along with the patients; they will receive the same dietary and physical activity education as patients, which can provide the basis for instrumental support and may benefit partners who are attempting weight loss themselves. These sessions will also include continued training in communication skills and social support principles with a focus on applying skills to the educational topic presented that month. Sessions will involve group discussion and role-plays around common challenges. Participants will be encouraged to share successes and challenges if they are comfortable doing so. There will also be breakout sessions so that couples can engage in guided exercises to identify individual challenges and preferred supportive behaviors and practice providing support (partner) and reinforcing this support (patients). During these meetings, couples will work together to generate a partner support plan to enhance support commitment. The interventionist and attending co-investigator will assist couples in this task.

#### **Partner involvement in weight loss maintenance intervention (months 7-18)**

Month 7 will involve partner attendance at the three patient group sessions led by the interventionist, which includes an overview of the patient maintenance program and a discussion of the partner's role in weight maintenance. Partners will co-participate in the three monthly calls in months 7-9 because it is important for partners to learn to work together effectively to promote patient behaviors that maintain weight loss and to receive coaching from the interventionist if challenges are encountered. Partners will also participate in calls in months 12 and 18. During all joint telephone calls, partners and patients will co-develop patient relapse plans and partner support plans. They will be encouraged to communicate regularly about the identified plans, assess progress, and work together to overcome barriers. Calls to couples will be ~10 minutes longer than patient-only calls. In the CouPLES trial, patients and spouses participated on >75% of calls together even though the protocol did not require it; thus, we expect high compliance in this study.

The content from the group sessions and maintenance telephone calls will be revised iteratively until the team feels that patients understand and can engage with the content. Changes may be made to enhance comprehension of intervention material or the ability to engage in the recommended behavioral skills.

#### **Text messages to reinforce intervention principles and reduce burden (months 1-18)**

Timing, frequency and development of message content are consistent with [name] previous successful research that is now being translated into clinical practice.(77) To recapture intervention principles, we will use text messages that we have developed and are currently implementing in our ongoing R34 (to patients in both arms) and support principles that were included in handouts from the CouPLES study (to partners in partner-assisted arm). These will be supplemented with patients' personalized goals and relapse prevention plans (to patients both arms) and partners' support plans (to partners in partner-assisted arm). In the maintenance period, the partner text messages will be the same as the patient text messages. Research staff will schedule the messages to be delivered over 18 months by Prompt. Table 6 shows the schedule and content by arm.

**Table 6**

Month	Frequency	Content	Sent To
1-6	3x/week	Initiation principles	Patients (both arms)
7-9	2x/week	Maintenance principles	
10-12	1x/week		
13-18	Every 2 weeks		
1-6	3x/week	Support principles, patients' dietary and activity goals, individual support plan	Partners (partner-assisted arm only)
7-9	2x/week	Support principles, patients' relapse prevention plans, individual support plan	Partners (partner-assisted arm only)
10-12	1x/week		
13-18	Every 2 weeks		

**Couples' communication sessions (patient-only arm)**

Following the 24-month outcome assessment, we will offer sessions 1 and 2 from the partner-assisted intervention to couples in the patient-only arm.

**9.2.3 Follow up:****Table 7.** Acceptable Window for Study Visits (including weekends)

Visit	Window	Activities
Screening visit	Up to 8 weeks prior to first group session	Informed consent, medical history/demographics, weight, dietary intake, physical activity, transformation of motivation, couples' efficacy, outcome efficacy, use of communal coping, social support for diet and physical activity, brief pain inventory-short form, COVID-19
Month 0	1st group session (0-8 weeks post screening visit)	Baseline weight is recorded, randomization status is revealed to participant.
Month 3	+/- 14 days from target assessment date	Transformation of motivation, couples' efficacy, outcome efficacy, use of communal coping, social support for diet and physical activity, COVID-19
Month 6	+/- 14 days from target assessment date	Weight, dietary intake, physical activity, transformation of motivation, couples' efficacy, outcome efficacy, use of communal coping, social support for diet and physical activity, brief pain inventory-short form, weight loss methods, COVID-19
Month 9	+/- 14 days from target assessment date	Transformation of motivation, couples' efficacy, outcome efficacy, use of communal coping, social support for diet and physical activity, COVID-19
Month 12	+/- 14 days from target assessment date	Weight, dietary intake, physical activity, transformation of motivation, couples' efficacy, outcome efficacy, use of communal coping, social support for diet and physical activity, brief pain inventory-short form, weight loss methods, COVID-19

Month 15	+/- 14 days from target assessment date	Transformation of motivation, couples' efficacy, outcome efficacy, use of communal coping, social support for diet and physical activity, COVID-19
Month 18	+/- 14 days from target assessment date	Weight, dietary intake, physical activity, transformation of motivation, couples' efficacy, outcome efficacy, use of communal coping, social support for diet and physical activity, brief pain inventory-short form, weight loss methods, COVID-19
Month 21	+/- 14 days from target assessment date	Transformation of motivation, couples' efficacy, outcome efficacy, use of communal coping, social support for diet and physical activity, COVID-19
Month 24	+/- 14 days from target assessment date	Weight, dietary intake and physical activity, weight loss methods

#### 9.2.4 Unscheduled:

- Unscheduled visits will not be included in this study.
- No concomitant therapies will be advised or suggested in this study.

#### 9.2.5 Final Study Visit

The final study visit will occur 24 months after enrollment. At the 24 month visit, the patient's weight, dietary intake and physical activity will be assessed via the methods described previously. We will have a two-week window on either side of the target assessment date.

No additional follow-up for AEs/SAEs will occur after the final outcome measurement visit due to minimal risk. Newsletters will be sent to all participants with study results summarized across participants. Patients will be aware of their weight measurements that occur at study visits, so individual disclosure of data is not necessary.

### 10. Study Analysis

#### 10.1 Sample Size Determination

The sample size estimate is based on the primary hypothesis that estimated patient weight will be at least 2.5 kg lower at 24 months in the partner-assisted than patient-only arm. This effect size was chosen because smaller differences are unlikely to be considered meaningful to researchers, providers, or patients.(78) The sample size was determined by multiplying the number of participants required for a t-test of post scores by 2(1-p) and adding one extra participant per arm.(79) Based on MAINTAIN, we anticipate a common standard deviation of 19.9 kg and a correlation (p) between the *month0* and *month24* time points of 0.96. Thus, we need 160 participants total (80 in each arm) to detect a 2.5 kg difference with 80% power and a type-I error rate of 5%. We further inflate the sample size to 1) incorporate the intra-class correlation (ICC) of small group members into consideration and 2) compensate for attrition using procedures for group-randomized designs.(66) Let  $m=15$  (conservative upper limit) be the number of patients in each of the small groups, and let  $ICC=0.01$  represent the intra-class correlation between patients in the same group. The updated sample size is  $n = 160 * [1 + (m-1)ICC]$ , or 180. We then conservatively inflate the sample size for an attrition rate of 20% through month24. Therefore, we will enroll  $n=230$  patients (115 per arm), randomized to receive the partner-assisted or patient-only intervention, to detect a 2.5 kg difference in mean 24-month net weight loss between arms.

#### 10.2 Statistical Methods

Descriptive statistics, including graphical displays, will be used to summarize all study variables. Distributional assumptions of the continuous outcome variables will be carefully examined and transformations made, if necessary. We will construct individual and mean trajectory plots of the longitudinal outcome variables to understand their general trends over the study period. In addition, we will explore the variability and correlation structure of the longitudinal outcome variables.

**Aim 1: Test the hypothesis that average patient weight is at least 2.5 kg lower in the partner-assisted arm than the patient-only arm at 24 months.** The unit of time will be months relative to randomization. The outcome is weight measured at each in-person study visit. Therefore, *month0* represents the weight at the point of randomization (i.e., the first group visit), and *month24* represents the primary study endpoint. The between-arm comparison in net weight loss from *month0* to *month24* will be examined with a multilevel longitudinal model(80) of the general form:  $Y_{ijt} = X_{ijt}\beta + c_j + Z_{ijt}b_{ij} + \varepsilon_{ijt}$ , where  $Y_{ijt}$  is weight in kg for patient  $i$  in small group  $j$  at  $t=month0, 6, 12, 18, 24$ . The predictors in the model will ( $X_{ijt}$ ) include a time main effect, the intervention main effect, and the intervention arm by time interaction, and  $Z_{ijt}$  will include an intercept and a time effect. We will use a flexible polynomial model for the main effect of time and keep the treatment by time interaction linear in time. We will first explore cubic time effects. If it is inadequate for the complexity in the temporal trend, higher order polynomials will be explored. We will formally check for the adequacy of a particular form for time effects using Wald or likelihood ratio tests for higher-order terms. The effect  $c_j$  is an additional random intercept for small group  $j$ , capturing common effects at the small group level. The predictor vector  $X_{ijt}$  will also include indicator variables for each of the eight strata defined by the cross-classification of the stratification variables of patient sex, patient BMI, and partner BMI. As a first step, the correlation of patients' repeated measures over time will be modeled and accounted for via the patient-level random intercept and time slope,  $b_{ij}$ . However, as is advised by good modeling practice,(80) various covariance structures for time will be explored, including unstructured and differential correlation structures by arm, via graphics such as the variogram and estimation with ReML,(81) all while being blinded to treatment effects. The AIC and BIC fit indices will be used to choose the best correlation structure. We will estimate the parameters in the model using the SAS procedure MIXED (Cary, NC). To test the null hypothesis that the average weight is equal in the two intervention arms, we will test if the coefficient for the time by treatment interaction is zero. Specifically, if  $X_{ijt}\beta$  takes the following form  $\beta_0 + \beta_1 trt + \beta_2 time + \beta_3 trt * t + \beta_4 covariates$ ,

where *trt* is the treatment indicator and *t* is linear time, then the null hypothesis is  $H_0: \beta_3 = 0$ . In addition, we will tabulate the analysis results for the (fixed) effects of the baseline covariates such as patient sex, patient BMI, and partner BMI.

**Aim 2: Test the hypotheses that average daily caloric intake is significantly lower, and frequency of moderate intensity physical activity is significantly greater, in the partner-assisted arm than the patient-only arm at 24 months.** Dietary adherence will be operationalized as daily intake of calories at months 0, 6, 12, 18, and 24. For each of these same assessment times, physical activity will be summarized as the total and mean minutes of moderate levels per week. Changes in dietary adherence and physical activity will be analyzed using the same methods and models as presented for the Aim 1 analyses of weight loss. Previous experience with these outcomes has shown they are often non-normally distributed; therefore, outcomes may be analyzed as generalized linear mixed models, estimated with adaptive Gaussian quadrature, as needed. As exploratory analyses, we will use the models described for Aims 1 and 2 to examine "spillover" effects(34) of the partner-assisted intervention on partner weight and dietary adherence.(50)

**Aim 3: Assess the extent to which interdependence constructs (transformation of motivation, couple efficacy, outcome efficacy, use of communal coping) mediate the effect of the partner-assisted weight management intervention on weight loss.** We will estimate the extent to which the effect of the partner intervention,  $T_i$  on participants' weight at 6 months,  $Y_i$ , is jointly mediated by a vector of five mediating constructs,  $M_i = (M_{i1}, \dots, M_{i5})$  measured at 3 months: transformation of motivation, couples' efficacy, outcome efficacy, use of communal coping, and social support. Each mediating construct is measured by the summary scale of associated items. We will assess mediation twice: separately for the diet and physical activity domains of the mediators.

Mediation analysis requires additional assumptions beyond treatment randomization, most importantly: (i) no unobserved mediator-outcome confounders; and (ii) no observed mediator-outcome confounder is affected by the intervention. In order to render assumption (i) more plausible, we will make statistical control for a vector of baseline values,  $B_i$  of the blocking variables, weight, and the mediating constructs, and we will assume that the block of mediators referring to diet and the block referring to physical activity do not affect each other (we do, however, permit that the elements of each  $M_i$  affect each other).

We will follow VanderWeele and Vansteelandt's approach to estimate the natural direct effect (NDE) and the natural indirect effect (NIE) of the intervention relative to a set of mediators,  $M$ , by estimating a set of regression equations.  $E[Y_i | T, M, B] = a_0 + a_1 T_i + a_{21} M_{i1} + \dots + a_{25} M_{i5} + a_3 B_i$

$$E[M_{ik} | T, B] = b_{0k} + b_{1k} T_i + b_{2k} B_i \text{ for } k = 1, \dots, 5.$$

We write  $Y_i(t, M_i(t'))$  for the potential outcome of  $i$  if  $i$  received intervention  $t$  and the value the mediators if  $i$  received intervention  $t'$ . Under assumptions (i), (ii), successful randomization of the intervention (all condition on  $B$ ), and correct functional form, we will then estimate the average natural direct effect of the intervention (versus not) on weight at 6 months as

$$E[Y_i(1, M_i(0)) - Y_i(0, M_i(0))|B] = a_1$$

and the natural indirect (mediation) effect as

$$E[Y_i(0, M_i(0)) - Y_i(0, M_i(1))|B] = b_{11}a_{21} + \dots + b_{15}a_{25}.$$

We will bootstrap the standard errors for the direct and indirect effects.

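### The sample size pays for small-group clustering of weight change, but the Aim 1 model carries groups only as a constant that cancels from the arm-by-time test

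*Combined protocol and SAP*

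**What the plan says.** Section 10.1 (repeated in section 8) sizes the trial "to detect a 2.5 kg difference in mean 24-month net weight loss between arms". It takes the n for a t-test of final weights, multiplies by 2(1-ρ), which is the variance factor for a change score, and reaches 160. It then inflates to "incorporate the intra-class correlation (ICC) of small group members into consideration", using 1+(m-1)ICC with m = 15 and ICC = 0.01, and states 180. Allowing for 20% attrition gives 230.

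Section 10.2 writes the Aim 1 model as fixed effects plus c_j, a patient-level term Z·b_ij and residual error. The group term c_j "is an additional random intercept for small group" j. Patients' repeated measures are handled "via the patient-level random intercept and time slope". For the primary hypothesis, "we will test if the coefficient for the time by treatment interaction is zero" (H0: β3 = 0, with time linear in the interaction). Aim 2 outcomes "will be analyzed using the same methods and models as presented for the Aim 1 analyses of weight loss".

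On delivery, section 9.2.2 says "Groups of ~11-12 patients will meet every 2 weeks". A patient's group slot follows from the randomised arm, so groups are nested in arm. In maintenance the programme "then switches mode from in-person to telephone, and finally decreases contact frequency". Table 3 places the last group session in month 9, and months 19-24 have no intervention contact.

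**The concern.** A design effect applied to a change-score sample size makes sense only if members of a group are correlated in weight change. The model's group term cannot represent that. It takes one value per group at every visit from month 0 to month 24, so it describes differences already present at the first session, before the group programme can act. Any divergence between groups during treatment is left to the patient-level slope, which the model treats as independent between patients.

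Because groups sit within arms, group differences in weight change add directly to the variance of the arm contrast. Leaving them out makes the primary interval too narrow and puts the type I error above 5%. The covariance search in section 10.2 does not close the gap. It concerns patients' repeated measures, names unstructured and arm-specific forms, and offers no group-by-time term for AIC or BIC to select.

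**Working it through.** **The plan's own figure.** With SD 19.9 kg, a difference of 2.5 kg, 80% power and two-sided 5% (sidedness is not stated; two-sided reproduces the result), a t-test of final weights needs 995 per arm. Then 995 × 2(1-0.96) = 79.6, plus 1 = 80.6 per arm, or about 160 in total. Next, 160 × [1 + 14 × 0.01] = 182.4 against the stated 180. Dividing by 0.8 gives 225 (from 180) or 228 (from 182.4), against the stated 230. The chain reproduces closely.

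**Inputs for the check.** From the plan: visits at 0, 6, 12, 18 and 24 months, and a change variance of 19.9² × 0.08 = 31.68 kg². About 20 groups follow from 230/11.5, so 10 per arm, with 11.5 × 0.8 = 9.2 completers per group. Assumed: residual SD 2 kg (also 1 and 3), and the shape of the group effect over time.

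**Why c_j cancels.** With complete data, β3 is the arm difference in mean patient slopes. Each slope weights the visits by (t-12)/360, where 360 = Σ(t-12)². These weights sum to zero, so a constant contributes nothing.

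The patient slope variance is (31.68 - 2×4)/576 = 0.0411. With n patients per arm, the model variance is

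Var(24β3) = (2/n) × 576 × (0.0411 + 4/360) = (2/n) × 30.08.

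This gives 0.668 kg² at 9 per group (n = 90) and 0.547 at 11 (n = 110). A full GLS calculation with cubic time gave the same values to within 0.001 for c_j variances of 0, 4, 20 and 400 kg². With 20% monotone dropout and groups of 11-12, the SE of 24β3 stayed at 0.769 kg for c_j variances of 0, 4 and 40.

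**True variance if groups differ in change.** Let the group variance at month 24 be ICC × 31.68, which is 0.317 kg² at ICC 0.01, with total variance held fixed. A group effect of shape g(t) enters 24β3 with multiplier k = 24 × Σ(t-12)g(t)/360. The ratio of true to model variance is 1 + (m-1) × k² × ICC × 31.68 / 30.08, and type I error is 2[1-Φ(1.96/√ratio)].

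| Group effect at months 0, 6, 12, 18, 24 | k | Variance ratio, m = 9 / 12 | Type I error |
|---|---|---|---|
| Linear growth | 1 | 1.084 / 1.116 | 6.0% / 6.4% |
| 0, 1, 1, 1, 1 | 0.8 | 1.054 / 1.074 | 5.6% / 5.9% |
| 0, 2, 1.67, 1.33, 1 | 0.533 | 1.024 / 1.033 | 5.3% / 5.4% |

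For example, linear growth with m = 9 gives 1 + 8 × 0.317/30.08 = 1.084.

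**Sensitivity.** Residual SD of 1 to 3 kg moves the linear row only to 5.9-6.5%. With linear growth and assumed larger ICCs, type I error is 7.0-7.7% at 0.02 and 10.0-11.9% at 0.05.

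**Simulation.** In 100,000 change-score trials analysed without regard to groups, type I error was 5.9% (9 per group) and 6.3% (12) at ICC 0.01. It was 6.9% and 7.7% at ICC 0.02, and 9.7% and 11.6% at 0.05. A t-test on group means with 18 df gave 4.8-5.1% throughout.

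**The case against.** Several points can be made for the plan.

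- **The ICC is not said to be for change.** Section 10.1 calls it only the correlation between patients in the same group. That is true. But if it does not act on change, the step from 160 to 180 has no bearing on the tested contrast, so the two sections still need reconciling.
- **The model is not closed.** Section 10.2 gives a general form and promises to explore covariance structures. This does not exclude a group slope, but it does not commit to one. Section 18 lists a separate Statistical Analysis Plan whose text was not available; it could contain the term.
- **The error is small and linear growth is unlikely.** Group sessions end in month 9, about 15 months before the primary endpoint. This stands: linear growth is the upper case of the three shapes, and the range at the plan's ICC is 5.3-6.4%.
- **The scaling matters.** All shapes are anchored to ICC 0.01 at month 24. The month-6 change variance is 36 × 0.0411 + 8 = 9.48 kg². The persisting shape therefore implies a month-6 ICC of 0.317/9.48 = 0.033, and the halving shape 4 × 0.317/9.48 = 0.13. Anchoring 0.01 at month 6 instead gives 5.2-5.3% (persisting), 5.0% (halving) and 10-12% (linear). This also stands: the documents cannot settle the size.
- **The remedy has its own cost.** With about 20 groups, a group variance bounded at zero combined with 18 df makes the test conservative, at 3.3-3.5%. This is why the rule for a zero estimate must be fixed in advance.
- **Aim 2 is not quantified.** No variances or ICCs are given for those outcomes, and the exact cancellation is shown only for the linear model.

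**Conclusion.** The concern holds. As written, the primary test makes no allowance for clustering of weight change, although the sample size does. The cancellation needs no assumption about the ICC. The size of the consequence does: it requires that groups differ in weight change, and it depends on how those differences evolve. At the plan's ICC of 0.01, taken at month 24 with about 20 groups, type I error is 5.3-6.4% and the true standard error is about 1-6% above the model's (√1.024 to √1.116). If groups differ only by a constant, the test is correct. The effect is modest, but it is anti-conservative, falls on the primary analysis, and arises from a correlation the sponsor chose to plan for. For Aim 2 the same structure applies, but its effect was not computed.

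**What to change.** In the Aim 1 equation, and in Aim 2, replace c_j with a small-group random intercept plus random time slope (c_0j + c_1j·t), or with a small-group-by-visit random effect. Use degrees of freedom that reflect about 20 groups: for example Kenward-Roger, or about 18 between-group df where Aim 2 is fitted by quadrature. State in advance what happens if the group slope variance is estimated as zero, for example an unbounded variance estimate (NOBOUND in PROC MIXED). If the separate Statistical Analysis Plan already has such a term, bring section 10.2 into line with it.

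The cost is SAP wording and one RANDOM statement; no extra patients are needed. There are three statistical costs.

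- **Wider interval.** With 184 completers (92 per arm) the SE of the change difference is 5.63 × √(2/92) = 0.830 kg, a half-width of 1.63 kg. The design effect 1 + 8.2 × 0.01 = 1.082 alone takes it to 1.69 kg. Moving from 1.96 to the t quantile on 18 df takes it to 1.81 kg, so most of the widening comes from the df.
- **Lower power.** For 2.5 kg on 18 df it is 78.2% (design effect 1.082) or 76.1% (1.14), against about 80-82% on patient-level df.
- **Frequent zero estimates.** With a true ICC of 0.01, the group variance is estimated as zero in about 41-44% of trials.
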